5.3 Exclusion Criteria

1. Disease Target Exclusion

- a) Patient has a history of basilar migraine or hemiplegic migraine

2. Medical History and Concurrent Diseases

- a) Patient history of HIV disease
- b) Patient history with current evidence of uncontrolled, unstable or recently diagnosed cardiovascular disease, such as ischemic heart disease, coronary artery vasospasm, and cerebral ischemia. Patients with Myocardial Infarction (MI), Acute Coronary Syndrome (ACS), Percutaneous Coronary Intervention (PCI), cardiac surgery, stroke or transient ischemic attack (TIA) during the 6 months prior to screening.
- c) Uncontrolled hypertension (high blood pressure), or uncontrolled diabetes (however patients can be included who have stable hypertension and/or diabetes for 3 months prior to being enrolled)
- d) Patient has a current diagnosis of major depression, other pain syndromes, psychiatric conditions (e.g., schizophrenia), dementia, or significant neurological disorders (other than migraine) that, in the Investigator's opinion, might interfere with study assessments
- e) Patient has a history of gastric, or small intestinal surgery, or has a disease that causes malabsorption

- f) The patient has a history or current evidence of any significant and/or unstable medical conditions (e.g., history of congenital heart disease or arrhythmia, known suspected infection, hepatitis B or C, or cancer) that, in the investigator's opinion, would expose them to undue risk of a significant adverse event (AE) or interfere with assessments of safety or efficacy during the course of the trial
 - g) History of, treatment for, or evidence of, alcohol or drug abuse within the past 12 months or patients who have met DSM-V criteria[15] for any significant substance use disorder within the past 12 months from the date of the screening visit
 - h) Patients should be excluded if they have a positive drug screen for drugs of abuse that in the investigator's judgment is medically significant, in that it would impact the safety of the patient or the interpretation of the study results. In addition:
 - i) Detectable levels of cocaine, amphetamine, and phencyclidine (PCP) in the drug screen are exclusionary. Patients who are positive for amphetamines on the urine drug screen may have their urine samples evaluated for further analysis at the investigator's discretion to rule out a false positive result.

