9.4 Statistical Methods

9.4.1 Primary Endpoint(s)

BHV-3000 (rimegepant) is tested for superiority to placebo, at an $\alpha=0.05$ level, on both pain freedom at 2 hours post-dose and freedom the most bothersome symptom at 2 hours post-dose. Both endpoints are evaluated using Cochran-Mantel Haenszel tests. The test for pain is stratified by the use of prophylactic migraine medication (yes or no). The test for the most bothersome symptom is also stratified by the use of prophylactic migraine medication (yes or no). These tests are conducted using the mITT subjects, with missing data at two hours imputed to be failure (i.e., Non-Completers = Failure; NC=F). Sensitivity analyses are described in the Statistical Analysis Plan (SAP).

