### **5.2.6 Subpopulations**

The subgroups of interest for this study:

- Age: Categorized as < 40, ≥ 40 years
- Race: white, black or African American, and other (certain tables may be created for the Asian population only; but in the subgroup analyses, Asian subjects will generally be included in the “other” category due to low counts)
- Sex: Female/Male
- Aura: Presence/Absence
- Headaches per Month: Categorized as < median, ≥ median
- Triptan Non-Responder: Yes/No
- CV Risk Contraindicating Triptans: Yes/No

Subgroup analyses will be performed for the primary endpoints only.

Triptan non-responders are identified using the “Prior Triptan Response” Case Report Form (CRF) pages. The definition of triptan non-responder is based on the number of triptans that a subject failed for efficacy reasons. For each triptan and route of administration, the subject is asked the questions shown in [Table 5](#). A subject is considered to have failed a drug for efficacy reasons if they indicated “most or all of the time” for any of the reasons in the table.

A triptan non-responder is defined as any subject that fails two or more molecular entities for efficacy reasons. To be considered a failure for a molecular entity, the subject must have failed on all routes of administration that the subject tried for the molecular entity.

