### 5.7.3.1 Pain Freedom at 2 Hours Post-Dose

Pain freedom is assessed using the number of mITT subjects that report pain levels of “none” at 2 hours post-dose on a 4-point Likert scale (0=none, 1=mild, 2=moderate, 3=severe). The information from the 4-point scale is directly summarized as follows:

- A table showing descriptive statistics for the observed data, which includes the number and percentage of subjects reporting each of the 4 pain levels at 2 hours post-dose, and the percentage of subjects with missing data, for each treatment group. The table will include exact (Clopper-Pearson) 95% CIs for each percentage.
  - This table will be repeated for Asian subjects only.

The estimand for the primary analysis is the percentage of pain free subjects. In statistical terms, this percentage is arrived at by estimating the probability or the “risk” that a subject is pain free.

The population summary, the between group difference in the percentage of pain free subjects is assessed by computing the “risk difference” between treatment groups. This is evaluated by computing the common risk difference, using Cochran-Mantel-Haenszel (CMH) weights (sample size weights), stratified by the use of prophylactic migraine medication (yes or no). The risk difference is tested at a two-sided alpha level of 0.05. Missing data at 2 hours post-dose will be imputed as failures (NC=F). If a stratum (prophylactic medication use: yes or no) has sparse data (less than 5 subjects), then the strata will be pooled.

Results presented for the primary analysis include the following:

- The number and percentage of subjects who are pain free, and those not pain free, at 2 hours post-dose. These are presented by stratum and treatment group, with asymptotic standard errors (ASE), and 95% asymptotic CIs.
- Common risk difference with sample size, p-value, asymptotic standard error (ASE), and 95% asymptotic CIs.
- Risk difference within each strata with sample size, p-value, asymptotic standard error (ASE), and 95% asymptotic CIs.
- A plot of the risk differences within each strata, and common risk difference (similar to the risk difference plot produced by SAS Proc Freq).
- Common risk for each treatment with sample size, ASE, and 95% asymptotic CIs.

The primary analysis will be repeated for the subgroups described in Section 5.2.6.

Sensitivity analyses will be conducted as follows:

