#### 5.7.3.2 *Freedom from MBS at 2 Hours Post-Dose*

Freedom from each subject's MBS is assessed using the number of mITT subjects who report that their MBS (reported at migraine onset) is absent at 2 hours post-dose. The symptoms that can be nominated as the MBS (phonophobia, photophobia or nausea) are measured using a binary scale (0=absent, 1=present).

Subjects who reported their MBS before taking IP, or who did not provide an MBS are considered failures in this analysis.

Tabulations will be presented as follows:

- The number and percentage of subjects reporting each of the migraine associated symptoms (phonophobia, photophobia or nausea) as most bothersome, subjects with a missing MBS, and subjects who reported their MBS after taking study medication.
- A cross tabulation of the historical MBS (reported at screening) as rows, and the MBS reported at the onset of the treated migraine as columns. This tabulation only includes subjects with both assessments. P-value from a chi-square test will be reported along with the values and confidence limits for both Asymmetric Lambda and Symmetric Lambda.

The estimand, difference in percentage of MBS free subjects (“risk difference”) between treatment groups, is evaluated by computing the common risk difference, using CMH weights (sample size weights), stratified by the use of prophylactic migraine medication (yes or no). The risk difference will be tested at a two-sided alpha level of 0.05. Missing data at 2 hours post-dose will be imputed as failure (NC=F). Also the use of rescue medication prior to providing data at the 2 hour assessment, taking IP prior to reporting the MBS, or failure to report a MBS are events that are imputed as treatment failures. If a stratum (prophylactic medication use: yes or no) has sparse data (less than 5 subjects) then the strata will be pooled.

The results to be presented for the primary analysis of MBS include those described in items (a) through (e) for the primary analysis of pain freedom (Section 5.7.3.1). In this case, the “risk” is now the probability of being MBS free at two-hours post-dose.

The primary analysis of MBS will be repeated for the subgroups described in Section 5.2.6.

Sensitivity analyses will be conducted as follows:

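### Subgroup and within-stratum results for the co-primary endpoints use asymptotic intervals whatever the row size; below about 20 subjects per arm these do not have 95% coverage

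*SAP*

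**What the plan says.** SAP 5.7.3.1 lists the output for pain freedom at 2 hours. It includes arm percentages by stratum with asymptotic standard errors and intervals, "Risk difference within each strata with sample size, p-value, asymptotic standard error (ASE), and 95% asymptotic CIs" and "Common risk difference with sample size, p-value, asymptotic standard error (ASE), and 95% asymptotic CIs". For sparse data it says: "If a stratum (prophylactic medication use: yes or no) has sparse data (less than 5 subjects), then the strata will be pooled". It does not say whether the 5 is a total or a count per arm. SAP 5.2.3, on pooling, adds no other protection.

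The whole set is carried to the seven subgroup factors of SAP 5.2.6: "The primary analysis will be repeated for the subgroups described in Section 5.2.6". SAP 5.7.3.2 uses the same output list and pooling rule for the most bothersome symptom (MBS): "The primary analysis of MBS will be repeated for the subgroups described in Section 5.2.6". The factors include "CV Risk Contraindicating Triptans: Yes/No". SAP Appendix 1 lists forest plots by subgroup for both endpoints (Figures 14.2.1.6 and 14.2.2.7).

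The exact (Clopper-Pearson) intervals in 5.7.3.1 apply to single-arm percentages in the observed-data table and its Asian-only repeat. None applies to a treatment difference, and no minimum subgroup size is set. Protocol 9.4.1 names a different test: "Both endpoints are evaluated using Cochran-Mantel Haenszel tests".

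**The concern.** An asymptotic interval for a difference in proportions relies on reasonable counts in both arms. The pooling rule does not secure that. A stratum of exactly 5 is analysed on its own, and a subgroup that has been pooled because it is tiny still gets asymptotic limits and a p-value.

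The visible failure is a row in which nobody responds. The estimated standard error is then 0 and the plotted interval collapses to a point at no difference, which looks like certainty when the data say almost nothing. The CV-risk row would attract attention, because limits on triptan use in cardiovascular disease are central to the rationale in protocol 1.4.

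**Working it through.** **Inputs.** Pain-freedom rates 31.4% and 15.3% (protocol 1.3.2.8 and 1.4.2), so the true difference is 0.161. Allocation 1:1 and about 550 treated per arm (SAP 2.2 and 5.1). MBS rates are not given; the component symptoms in protocol 1.4.2 serve as an assumed range: photophobia 41.9% v 24.1%, phonophobia 52.3% v 28.1%, nausea 67.4% v 51.2%. The SAP says asymptotic without naming a formula. I take the Wald form, which fits its standard error and its reference to SAS Proc Freq. The Sato (Mantel-Haenszel) variance gives the same results in a single-stratum row.

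**Full trial first.** The pooled rate is (0.314 + 0.153)/2 = 0.2335. The null standard error is √(2 × 0.2335 × 0.7665/550) = 0.0255 and the alternative one is √((0.314 × 0.686 + 0.153 × 0.847)/550) = 0.0250. Power is Φ((0.161 − 1.96 × 0.0255)/0.0250) = Φ(4.4), above 99.99%. The plan's figure of more than 95% holds. Simulated coverage of the common risk difference at full size (assumed strata of 120 and 980) is 94.9%. The method is sound there.

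**Small rows.** The interval is d ± 1.96 √(p̂₁(1−p̂₁)/n₁ + p̂₂(1−p̂₂)/n₂). Its exact coverage is the sum of Bin(a; n₁, 0.314) × Bin(b; n₂, 0.153) over all outcomes (a, b) whose interval contains 0.161.

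| Per arm | Wald coverage | Zero width | Newcombe coverage |
|---|---|---|---|
| 5 | 75.7% | 6.8% | 95.6% |
| 10 | 91.6% | 0.4% | 95.0% |
| 20 | 93.1% | <0.1% | 95.7% |
| 30 | 94.3% | <0.1% | 95.0% |
| 50 | 94.6% | <0.1% | 95.2% |
| 100 | 94.8% | <0.1% | 95.1% |

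If the 5 is a total, a stratum split 2/3 (rimegepant/placebo) is allowed: coverage 62.4%, zero width 34.8%.

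**Zero width by hand at 5 per arm.** (0.686⁵ + 0.314⁵) × (0.847⁵ + 0.153⁵) = 0.155 × 0.436 = 6.8%. With 15.3% in both arms, the chance of no responders at all is 0.847¹⁰ = 19%. For 0/5 v 0/5 the Wald interval is [0, 0]; Newcombe gives −43 to +43 points.

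**Arm percentages.** With 5 placebo subjects, only 1 or 2 responders give a Wald interval containing 15.3%. Coverage is 5 × 0.153 × 0.847⁴ + 10 × 0.153² × 0.847³ = 0.394 + 0.142 = 54%.

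**Assumed MBS rates.** Wald coverage is 83–89% at 5 per arm, 90–93% at 10 and 93–94% at 20.

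**Common risk difference in a subgroup** (simulated, Sato / unpooled variance). Strata of 5 and 5 in total: 87.9% / 81.9%. Strata of 5 and 20: 92.9% / 91.5%. Strata of 5 and 100: 94.5% / 94.3%. A tiny stratum inside a large subgroup therefore spoils its own row and hardly moves the common estimate.

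**Test size.** With 15.3% in both arms, the Wald test rejects 2.6% of the time at 5 per arm, 8.0% at 10 and 5.9% at 30.

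**The case against.** The strongest reply is that no document shows a subgroup this small will occur. Twenty per arm is 40 of about 1,100 treated, or 3.6%. The splits by age and by median headache frequency are not shown to be anywhere near that. This stands: the fault lies in the rule as written, and whether it bites depends on counts not in the documents.

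A reader might infer that the CV-risk group must be tiny, since protocol 5.3 excludes "Patient history with current evidence of uncontrolled, unstable or recently diagnosed cardiovascular disease" and also uncontrolled hypertension, itself a qualifying item in SAP 5.2.6. But protocol 5.2 admits patients with triptan contraindications, and protocol 1.4.1 expects cardiovascular comorbidity to be represented. Small is plausible, not established. Nor does the low count of Asian subjects prove the point: the SAP generally merges them into the other-race category for subgroup analyses, and its Asian-only table uses exact limits.

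A reader might also infer that the intervals are always too narrow and the tests always too liberal. Neither holds. At 5 per arm and photophobia rates, mean Wald width is 1.00 against 0.89 for Newcombe, yet Wald coverage is only 87.5%. The rejection rates above fall on both sides of 5%.

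Newcombe is not perfect either. At 5 per arm and photophobia rates the same enumeration gives it 91.9%, and at 20 per arm and phonophobia rates it gives 93.4% against 94.1% for Wald. It avoids the collapse to zero width and the worst under-coverage; it does not guarantee 95% everywhere.

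Finally, sample sizes are shown with the results, and SAP 5.2.5 places no subgroup in the testing hierarchy. That limits the consequence.

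**Conclusion.** The point holds, as a minor one. In any subgroup or stratum row with fewer than about 20 subjects per arm, the planned interval labelled 95% is miscalibrated. Coverage at the Phase 2b pain-freedom rates is about 76% at 5 per arm and 92% at 10, and it is close to nominal from 30 to 50. The other-race group, the CV-risk group and their strata on prophylaxis are the plausible places, but none is shown to be that small.

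Large subgroups and the co-primary tests are unaffected. The full-trial strata should be too, unless very few subjects use prophylaxis. No confirmatory claim rests on the affected rows; the harm is misleading descriptive intervals and p-values. The figures assume Wald limits, Phase 2b rates and, except in the 2/3 example, equal arms. The MBS figures also assume that component-symptom rates stand in for MBS rates.

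**What to change.** In SAP 5.7.3.1 and 5.7.3.2, leave the primary analysis as it is. For the subgroup and within-stratum rows:

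- Use Newcombe or Miettinen-Nurminen score intervals for the risk difference, in the stratified version for a subgroup's common difference.
- Use Wilson or Clopper-Pearson intervals for the arm percentages.
- Take p-values from the Cochran-Mantel-Haenszel test named in protocol 9.4.1, or from an exact test where the row is sparse. The former is itself asymptotic and is undefined when nobody responds, so report the p-value as not estimable in that case.
- State whether the pooling threshold of 5 is a total or a count per arm.

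The cost is SAP wording and a small programming change to the subgroup and stratum outputs. Large rows barely change. Small rows will show different intervals, often but not always wider.

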#### 5.7.3.2 *Freedom from MBS at 2 Hours Post-Dose*

Freedom from each subject's MBS is assessed using the number of mITT subjects who report that their MBS (reported at migraine onset) is absent at 2 hours post-dose. The symptoms that can be nominated as the MBS (phonophobia, photophobia or nausea) are measured using a binary scale (0=absent, 1=present).

Subjects who reported their MBS before taking IP, or who did not provide an MBS are considered failures in this analysis.

Tabulations will be presented as follows:

- The number and percentage of subjects reporting each of the migraine associated symptoms (phonophobia, photophobia or nausea) as most bothersome, subjects with a missing MBS, and subjects who reported their MBS after taking study medication.
- A cross tabulation of the historical MBS (reported at screening) as rows, and the MBS reported at the onset of the treated migraine as columns. This tabulation only includes subjects with both assessments. P-value from a chi-square test will be reported along with the values and confidence limits for both Asymmetric Lambda and Symmetric Lambda.

The estimand, difference in percentage of MBS free subjects (“risk difference”) between treatment groups, is evaluated by computing the common risk difference, using CMH weights (sample size weights), stratified by the use of prophylactic migraine medication (yes or no). The risk difference will be tested at a two-sided alpha level of 0.05. Missing data at 2 hours post-dose will be imputed as failure (NC=F). Also the use of rescue medication prior to providing data at the 2 hour assessment, taking IP prior to reporting the MBS, or failure to report a MBS are events that are imputed as treatment failures. If a stratum (prophylactic medication use: yes or no) has sparse data (less than 5 subjects) then the strata will be pooled.

The results to be presented for the primary analysis of MBS include those described in items (a) through (e) for the primary analysis of pain freedom (Section 5.7.3.1). In this case, the “risk” is now the probability of being MBS free at two-hours post-dose.

The primary analysis of MBS will be repeated for the subgroups described in Section 5.2.6.

Sensitivity analyses will be conducted as follows:

1. The primary analysis is repeated, once using the mITT subjects that had a qualifying migraine before the last relevant software fix was applied to the eDiaries (onset on or before 13-Sep-2017), and once for mITT subjects with migraine onset dates after the software fix was applied (onset after 13-Sep-2017).
2. The primary analysis is repeated, using the mITT population, with missing data at 2 hours post-dose imputed using Last Observation Carried Forward (LOCF). Baseline Observation Carried forward is permitted.
3. The primary analysis is repeated, using only data from complete cases (data present at baseline and 2 hours).
4. The primary analysis is executed using the mITT analysis set, and multiple imputation (with 20 imputations;  $m=20$ ) methods to impute missing data at 2 hours post-dose using the copy from reference approach. The FCS method is used with a generalized logit distribution. Covariates may include use of prophylactic medication (yes or no), sex, migraine intensity at onset (severe or other), migraines per month ( $<$  median,  $\geq$  median), date of migraine onset (on or before 13-Sep-2017 or after 13-Sep-2017), and the subject’s MBS at time of study migraine onset (nausea, photophobia, or phonophobia).

5. A matrix of “what if” analyses, similar to that created for the co-primary endpoint of pain freedom, is created for freedom from the MBS.
6. The primary analysis will be repeated, using the mITT population, with the addition of a strata that reflects the subject’s self-reported MBS at the time of study migraine onset (nausea, phonophobia, or photophobia).

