3 STUDY ENDPOINTS

3.1 Primary

Pain freedom will be assessed using the number of evaluable subjects that report no pain at 2 hours post-dose. Pain will be measured on a 4 point Likert scale (0=none, 1=mild, 2=moderate, 3=severe).

Freedom from the most bothersome symptom (MBS) will be assessed using the number of evaluable subjects that report the absence of their MBS at 2 hours post-dose. The MBS (nausea, phonophobia or photophobia) will be measured using a binary scale (0=absent, 1=present).

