6.3.2 Nausea, Phonophobia and Photophobia

The migraine associated symptoms of photophobia, phonophobia and nausea are measured on a two point scale (present or absent), using the eDiary, at the time points listed in [Table 1](#). If a subject reports the presence of a symptom, the subject is then asked to rate the severity of the symptom on a four point scale (none, mild, moderate or severe). All assessment is done using the eDiary.

The subjects are also asked to identify their most bothersome symptom on the eDiary (nausea, phonophobia or photophobia) at the onset of the migraine to be treated. The most bothersome symptom must be identified before the subject takes study medication.

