**Table 1: Estimands for the Co-Primary Objectives**

Objective	Pain Freedom at 2 hours post-dose
Population	mITT
Variable	Percent of subjects reporting no pain at 2 hours post-dose
Intercurrent Events	NC=F; RM=F;
Objective	Freedom from Most Bothersome Symptom (MBS)
Population	mITT
Variable	Percent of subjects reporting absence of their MBS at 2 hours post dose
Intercurrent Events	NC=F; RM=F; Failure to report MBS = F; Study medication taken before reporting MBS=F.

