##### **5.7.4.1 Freedom from Photophobia, Phonophobia or Nausea at 2 Hours**

Freedom from photophobia, phonophobia, and nausea are assessed, by treatment group, by tabulating the number of mITT subjects who reported the presence of the symptom at migraine onset who then report the absence of the symptom at 2 hours post-dose. Subjects who report the symptom at baseline, but have missing data at 2 hours post-dose will be imputed as failures (NC=F). Also, subjects in the analysis set that take rescue medications on or before providing their 2 hours post-dose data are imputed as failures.

The principal measurement for the associated symptoms (phonophobia, photophobia, and nausea) is made on a binary scale (0 = absent; 1 = present). An exploratory measurement of these symptoms was also made on a 4 point Likert scale (0=none, 1=mild, 2=moderate, 3=severe).

For these three endpoints, the difference between treatment groups, is evaluated by computing the common risk difference, using CMH weights (sample size weights), stratified by the use of prophylactic migraine medication (yes or no). The risk difference is tested at a two-sided alpha level of 0.05. If a stratum (prophylactic medication use: yes or no) has sparse data (less than 5 subjects) then the strata are pooled.

The results presented for the analysis of each symptom include those described in items (a) through (e) for the primary analysis of pain freedom (Section 5.7.3.1). In this case, the “risk” is the probability of being free from the symptom of interest at 2 hours post-dose. In addition, the following display will be created for each of the 3 symptoms:

- A table showing descriptive statistics for the 4-point scale, which includes the number and percentage of subjects reporting each of the 4 symptom levels at 2 hours post-dose, and the percentage of subjects with missing data, for each treatment group. The table will include exact (Clopper-Pearson) 95% CIs for each percentage.

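### As written, the MBS co-primary can be met by a subject who recorded the nominated symptom as absent at onset, because presence at onset is not required

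*SAP*

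**What the plan says.** Protocol 3.1 bases the second co-primary on the number of "evaluable subjects that report the absence of their MBS at 2 hours post-dose". SAP Table 1 gives the variable as "Percent of subjects reporting absence of their MBS at 2 hours post dose" in the mITT population, and SAP 5.7.3.2 says the endpoint is "assessed using the number of mITT subjects who report that their MBS (reported at migraine onset) is absent at 2 hours post-dose".

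SAP Table 1 lists the events handled as failures: "NC=F; RM=F; Failure to report MBS = F; Study medication taken before reporting MBS=F". That is missing data, rescue medication, no MBS named, and drug taken before the MBS was named. The mITT definition (SAP 4.1) asks for moderate to severe baseline pain and one post-baseline efficacy value. It does not ask for any associated symptom.

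Protocol 6.3.2 describes symptom presence (present or absent) and the choice of MBS as separate eDiary items. The choice is among nausea, phonophobia and photophobia, and the instruction is: "The most bothersome symptom must be identified before the subject takes study medication".

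The single-symptom secondary endpoints are defined differently. SAP 5.7.4.1 counts "mITT subjects who reported the presence of the symptom at migraine onset who then report the absence of the symptom at 2 hours post-dose".

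**The concern.** The co-primary is meant to show that the symptom troubling the patient most went away. Under the written rule, a subject whose nominated symptom was recorded absent at onset can be counted as MBS-free although nothing resolved. Pain freedom does not have this weakness, because mITT guarantees pain at baseline. Nor do the three symptom endpoints, because they are limited to subjects with the symptom at onset. Among these 2-hour freedom endpoints, only the MBS co-primary can record success with no change.

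What is at stake is the meaning of the reported rates. Such subjects raise the MBS-free rate in both arms, shrink the difference, and add some sensitivity to how many of them fall in each arm.

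**Working it through.** **1. Does any rule catch the case?** Take a subject who names photophobia before dosing, records photophobia absent at onset and at 2 hours, and takes no rescue medication before the 2-hour report.
- The four failure rules do not apply: data are present, no rescue was taken, an MBS was named, and it was named before dosing.
- Sensitivity analyses 1 to 6 in SAP 5.7.3.2 do not apply a presence condition. They split by date of the software fix, use LOCF, use complete cases (baseline data must exist, but the symptom need not be present), use multiple imputation, vary assumed rates for missing data, and stratify by MBS type.
- In sensitivity analysis 2, "Baseline Observation Carried forward is permitted". A carried-forward baseline value of absent would then be a success. For pain it cannot be, since baseline pain is moderate or severe.
- Appendix 4 repeats the pattern. The MBS durability and time-to-event analyses use all mITT subjects, while the single-symptom versions require presence at onset.

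One sentence in SAP 5.7.3.2 classes subjects who named their MBS before taking drug as failures. SAP Table 1, SAP 5.7.2 and a later sentence of 5.7.3.2 say the opposite, so I read it as a drafting slip.

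**2. The plan's own power figure.** Protocol 9.2 and SAP 5.1 state more than 95% power per co-primary with 550 per group, and at least 90% jointly. No Phase 2b MBS rate is given, so I use the single-symptom rates in Protocol 1.4.2 as proxies. Power = Φ[(d − 1.96·SE₀)/SE₁], with SE₀ from the pooled rate and SE₁ from the separate rates.
- Photophobia, 41.9% vs 24.1%: d = 0.178; SE₀ = √(2 × 0.33 × 0.67/550) = 0.0284; SE₁ = √[(0.419 × 0.581 + 0.241 × 0.759)/550] = 0.0278. Power is above 99.99%.
- Nausea, 67.4% vs 51.2%: 99.98%.
- Phonophobia, 52.3% vs 28.1%: above 99.99%.
- Joint lower bound: 1 − 0.05 − 0.05 = 0.90.

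The stated figures are met. They also hold at 600 × 0.90 = 540 per arm, where the lowest is 99.97%.

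**3. Effect of the gap.** Let f be the share of subjects whose nominated symptom was absent at onset, equal in both arms, all of them recording it absent at 2 hours. The documents give no value for f, so the values below are assumptions. Let p be the true freedom rate among the rest. The reported rate is f + (1 − f)p, and the difference is (1 − f) times the true difference. With the photophobia proxy:

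| f | Rimegepant | Placebo | Difference (points) |
|---|---|---|---|
| 0 | 41.9% | 24.1% | 17.8 |
| 5% | 44.8% | 27.9% | 16.9 |
| 10% | 47.7% | 31.7% | 16.0 |
| 20% | 53.5% | 39.3% | 14.2 |

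With no drug effect and equal f, the two rates are equal and the expected difference is zero. At f = 20% the lowest power across the three proxies is 99.6% (nausea).

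**4. Alternatives at f = 10%, photophobia proxy.**
- As written: difference 0.160; SE = √[(0.477 × 0.523 + 0.317 × 0.683)/550] = 0.0291; ratio 5.5.
- Coded as failures, rate (1 − f)p: 37.7% vs 21.7%; difference 0.160; SE = √[(0.377 × 0.623 + 0.217 × 0.783)/550] = 0.0271; ratio 5.9.
- Restricted to symptom present at onset, 550 × 0.9 = 495 per arm: difference 0.178; SE = √[(0.419 × 0.581 + 0.241 × 0.759)/495] = 0.0293; ratio 6.1.

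Failure coding lowers the SE but leaves the dilution. Only restriction removes it. For a smaller assumed effect that is not in the documents (35% vs 27%, f = 10%), unpooled-SE power is 69% as written and 76% with failure coding.

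**5. Imbalance.** A 2-point difference in f between arms moves the result by 0.02 × (1 − p): 1.2 points at p = 0.419 and 1.5 at p = 0.241. Under failure coding it moves by 0.02 × p: 0.8 and 0.5 points.

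**The case against.** The strongest reply is that the case may be rare or impossible. The Schedule of Assessments (footnote 2) and Protocol 4.3.2 ask for the current MBS. The typical MBS is a separate screening item (footnote 14). Read normally, a current most bothersome symptom is a present one. Protocol 1.4 describes migraine attacks as associated with nausea or vomiting and/or sensitivity to sound and light. If the eDiary offers only symptoms marked present, the case cannot arise. This stands as a limit on frequency. It does not repair the definition, because neither document describes such a check.

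A reader might infer that a headache-only subject is forced to name a symptom and so becomes an automatic success. The documents do not support that. The SAP expects subjects with no MBS: Table 1 fails them, 5.7.3.2 tabulates them, and 5.6 has a category for MBS not reported. Success also needs an absent report at 2 hours and no earlier rescue.

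It is also fair that chance imbalance in f is ordinary sampling variation already in the SE, and that the baseline carry-forward route is narrow, since it needs no symptom value from 15 minutes through 2 hours. Presence-restricted evidence is already planned, as tests 1, 2 and 4 of the hierarchy. Finally, failure coding replaces overstated rates with understated ones. That is why a restricted analysis belongs beside it.

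**Conclusion.** The gap is real as a matter of the written rule. SAP Table 1, SAP 5.7.3.2 and Protocol 3.1 allow success on a co-primary with no change from onset, and nothing else in the plan catches it.

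Its likely effect is modest. With an equal share in both arms, both MBS-free rates rise and the difference is multiplied by (1 − f): 17.8 to 16.0 points at an assumed 10% with the photophobia proxy. A reader might infer that the rule favours rimegepant or threatens the stated power. Neither follows. With equal shares the expected difference under no effect is zero, so type I error is not inflated, and power stays above 99% under the Phase 2b proxies even at 20%.

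These figures rest on an assumed f, on every such subject recording absent at 2 hours, and on single-symptom rates standing in for an MBS rate that the documents do not give.

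**What to change.** Before unblinding:
- In SAP Table 1 and 5.7.3.2, define MBS-free as *nominated MBS recorded present at onset and absent at 2 hours*, and add *nominated MBS recorded absent at onset = F* to the failure rules.
- Apply the same rule in the LOCF/BOCF sensitivity analysis and the Appendix 4 MBS analyses.
- Tabulate these subjects by arm in Table 14.2.2.
- Add a sensitivity analysis restricted to mITT subjects whose nominated MBS was present at onset, since failure coding does not remove the dilution.

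If the data are already unblinded, leave the co-primary as it is and add the tabulation and the restricted analysis, labelled post hoc. The SAP's summary of changes says V2.0 added post-hoc analyses, so this may be the branch that applies. If the eDiary limits the MBS list to symptoms marked present, a sentence in the SAP saying so would close the point.

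The cost is SAP wording, one derivation from onset data already collected, and one extra analysis. Failure coding keeps the mITT denominator and matches the existing treatment of subjects who name no MBS. The downside is slightly lower reported MBS-free rates in both arms.
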